3.0 STUDY REFERENCE INFORMATION

3.1 Study-Related Responsibilities

The sponsor will perform all study-related activities with the exception of those identified in the Study-Related Responsibilities. The vendors identified in the template for specific study-related activities will perform these activities in full or in partnership with the sponsor.

3.2 Principal Investigator/Coordinating Investigator

Takeda will select a Signatory Coordinating Investigator from the investigators who participate in the study. Selection criteria for this investigator will include significant knowledge of the study protocol, the study drug, their expertise in the therapeutic area, and the conduct of clinical research as well as study participation. The Signatory Coordinating Investigator will be required to review and sign the clinical study report and by doing so agrees that it accurately describes the results of the study.

3.3 List of Abbreviations

5-HT serotonin
AE adverse event

ALT alanine aminotransferase AST aspartate aminotransferase

CGI-I Clinical Global Impression Scale-Improvement
CGI-S Clinical Global Impression Scale-Severity

CRO contract research organization

C-SSRS Columbia-Suicide Severity Rating Scale

DRESS drug reaction with eosinophilia and systemic symptoms

DSM-5 Diagnostic and Statistical Manual of Mental Disorders, Fifth Edition

omp Company Confidential Information

ECG electrocardiogram

electronic case report form

full analysis set

FSH follicle-stimulating hormone
GAS Goal Attainment Scale
GCP Good Clinical Practice

hCG human chorionic gonadotropin

ICH International Council for Harmonisation

ID identification

IEC independent ethics committee
INR international normalized ratio
IRB institutional review board

IxRT Interactive Response Technology

ompan Company Confidential Information

liver function tests

major depressive disorder major depressive episode

MedDRA Medical Dictionary for Regulatory Activities

PGx pharmacogenomics

PDQ-D Perceived Deficits Questionnaire-Depression

PHQ-9 Patient Health Questionnaire-9

PPS per protocol set PTE pretreatment event

Q-LES-Q Quality of Life and Enjoyment and Satisfaction Questionnaire

QD once daily

Company Confidential Information

serious adverse event

Sirs
Stevens-Johnson syndrome
Informati

CONFIDENTIAL

STAR*D Sequenced Treatment Alternatives to Relieve Depression

SUSAR suspected unexpected serious adverse reaction

TEN toxic epidermal necrolysis

UDS urine drug screen
ULN upper limit of normal

US United States

Company Confidential Information

WAIS-IV Wechsler Adult Intelligence Scale Fourth Edition

World Health Organization

WHO-5 5-item World Health Organization Well-Being Index

3.4 Corporate Identification

TDC Japan Takeda Development Center Japan

TDC Asia Takeda Development Center Asia, Pte Ltd
TDC Europe Takeda Development Centre Europe Ltd.
TDC Americas Takeda Development Center Americas, Inc.

TDC Japan, TDC Asia, TDC Europe and/or TDC Americas, as applicable
Takeda TDC Japan, TDC Asia, TDC Europe and/or TDC Americas, as applicable

4.0 INTRODUCTION

4.1 Background

According to the World Health Organization (WHO), depression accounts for 4.3% of the global burden of disease and is among the largest single causes of disability worldwide (11% of all years lived with disability globally) [1]. Specifically in the United States, the prevalence of major depressive disorder (MDD) is currently 8.3%, with expectations that prevalence will increase over the coming years [2].

The economic consequences of MDD are significant. The ability of depressed patients or their caregivers to work and make productive contributions to the economy is reduced, while the use of treatment and support services is increased. A recent study estimated that the cumulative global impact of mental disorders in terms of lost economic output will amount to US \$16.3 million between 2011 and 2030 [1].

Depression is recurrent in 75% to 80% of patients and becomes chronic (lasts 2 years or longer) in 15% to 20% of depressed patients [3,4]. Furthermore, depression can lead to substantial impairments in an individual's ability to take care of his/her everyday responsibilities and approximately 15% of depressed patients commit suicide [5]. Unfortunately, the risk of relapse of recurrence, chronicity (as measured by the duration of episodes), and treatment resistance increases with each new episode. Thus, treatment to full remission and continued treatment to prevent relapse and recurrence are both major priorities for management of recurrent MDD [6,7].

4.1.1 Vortioxetine

Vortioxetine is an antidepressant agent approved in 2013 in the United States and the European Union for treatment of MDD. It differs from preexisting antidepressants in that it combines 2 pharmacological modes of action: direct modulation of receptor activity and inhibition of the serotonin transporter. Vortioxetine is an antagonist at 5-HT3, 5-HT7, and 5-HT1D receptors, an agonist at 5-HT1A receptors, a partial agonist at 5-HT1B receptors, and an inhibitor of the 5-HT transporter [8,9]. The following sections briefly review the results from nonclinical and clinical studies of vortioxetine.

4.1.1.1 Nonclinical Background

Preclinical studies concluded that vortioxetine had a difference pharmacological profile than other selective serotonin reuptake inhibitors) and serotonin noradrenaline reuptake inhibitors. Key pharmacological differences include its interaction with 5-HT targets which modulates multiple neurotransmitter systems, the reversal of cognitive deficits in various animal models, and its effects in depression models [10].

4.1.1.2 Clinical Background

During the clinical development program, the efficacy, safety, and tolerability of vortioxetine in MDD subjects was evaluated at doses from 1 to 20 mg once daily (QD) in short-term efficacy

studies of 6 to 8 weeks duration and long-term safety studies up to 52 weeks duration. Vortioxetine was safe and well-tolerated across the dose range. The efficacy of vortioxetine in the treatment of MDD was established in 6- to 8-week randomized, double-blind, placebo-controlled, fixed-dose studies (including 1 study in the elderly). Efficacy was established at doses of 5, 10, 15, and 20 mg with the recommended starting dose being 10 mg/day [11].

4.2 Rationale for the Proposed Study

After unsuccessful treatment with initial antidepressant monotherapy treatment of adequate dose and duration, clinical practice guidelines for the treatment of MDD recommend changing the antidepressant. This treatment change may be necessary when patients respond poorly to antidepressant medication or exhibit intolerable side effects.

Data from clinical studies regarding switching antidepressant medication rates is minimal and the rationale for the switch varies across studies [12]. Claims databases have shown switching rates for antidepressants have ranged from 2.78% to 13.7% [13,14]. The results of switching, in particular, multiple switching can lead to suboptimal outcomes for patients. Results of the Sequenced Treatment Alternatives to Relieve Depression (STAR*D) study showed that as the number of switches increased the burden of illness, including relapse rates, also increased. Relapse may trigger a pharmacologic switch [15]. Switching antidepressant agents has been shown to increase treatment costs and can be burdensome to the patient, so it is important to get the patient to the optimal treatment as early as possible in the therapeutic pathway [16].

A process used in the mental health arena to assess and capture the patient's experience regarding whether or not treatment is successful is Goal Attainment Scaling; however, this approach has not been widely used in assessing the treatment of depression or in clinical research. Goal Attainment Scaling was first developed by Thomas Kiresuk and Robert Sherman in response to the wide variety of evaluation models regarding mental illness and treatment [17]. Goal Attainment Scaling has long been used in clinical care and program assessment to evaluate patient progress and ensure alignment between clinician and patient on treatment objectives [17]. Through a structured interview and goal setting between clinician and patient, the Goal Attainment Scaling process captures meaningful aspects of a person's progress throughout the course of treatment that are challenging to assess using available standardized measures. The aim of this study is to demonstrate that the process of Goal Attainment Scaling in MDD in conjunction with a change in antidepressant treatment to vortioxetine is effective in achieving outcomes that matter to patients, improves quality of life and is an effective strategy to treat MDD when the current or recent antidepressant is not adequate.

5.0 STUDY OBJECTIVES AND ENDPOINTS

5.1 Objectives

5.1.1 Primary Objective

To determine the effectiveness of treatment with vortioxetine on subject goal achievement after a change in antidepressant medication for the treatment of MDD.

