6.0 STUDY DESIGN AND DESCRIPTION

6.1 Study Design

This study is an open-label, single-arm, multicenter, prospective, phase 4, interventional, flexible-dose study (as per the Trintellix US package insert) to determine the effectiveness of treatment with vortioxetine on subject goal achievement after a change in antidepressant medication for the treatment of MDD.

This study is comprised of a 3-week Screening Period (maximum 21 days), to be followed by a 12-week Treatment Period and a 4-week Safety Follow-up Period. Study visits will occur at Baseline (Day 1), and Weeks 2, 4 (Telephone), 6, 9 (Telephone), and 12. This study will enroll approximately 120 subjects and will be conducted at approximately 25 sites in the United States.

This study will enroll men and women between the ages of 18 and 65, inclusive, with a primary diagnosis of MDD, who have previously been treated within 6 weeks of Screening or are currently being treated for a major depressive episode (MDE) with an approved antidepressant for 6 weeks or longer at an adequate dose. Subjects who are dissatisfied with their current or recent antidepressant and are interested in a change in antidepressant treatment will be eligible for Screening.

The change in antidepressant medication will be based on the investigator's judgment in collaboration with the subject's level of dissatisfaction with their current or recent antidepressant treatment (ie, residual mood symptoms, intolerable side effects). Subjects also need to be eligible per the Trintellix United States (US) package insert and sign and date a written, informed consent form and any required privacy authorization prior to the initiation of any study procedures.

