The investigator or the investigator's designee will access the Interactive Response Technology (IxRT) at Screening to obtain the subject study number. At the Baseline Visit, if the subject has satisfied all of the inclusion criteria and none of the exclusion criteria for enrollment, the subject will be enrolled using the IxRT. Subjects will be instructed on when to take the first dose of study drug. The dosing (both initial and adjustments) will be determined by investigator or designee as per routine clinical practice and per approved Trintellix labeling. Subjects will determine treatment goals with their clinicians using the GAS adapted for an MDD population. The subject and clinician will work to establish 3 goals at Baseline. One goal will be determined based on the subject's self-defined objectives. Two goals will be selected from the following predefined categories representing MDD residual symptoms, antidepressant side effects, and common reasons for a change in antidepressant medication, including but not limited to:

[figure not shown]
MDD Domains	Psychological	Motivation	Emotional	Physical/ Functional	Cognition
Predefined goal categories:	-Depressed mood -Anxious mood	-Lack of motivation	-Low self esteem -Anhedonia	-Fatigue -Insomnia -Muscle tension -Sexual dysfunction -Weight gain	-Problems concentrating -Short term memory problems -Difficulty staying focused -Difficulty paying attention -Problems thinking clearly

[figure not shown]
A prepopulated list of categories will be provided in the structured guidance for goal assessment, including behavioral examples describing goals and observable benchmarks to help clinicians set the appropriate goals with subjects. Goals will be set at Baseline/Visit 1. Progress will be evaluated at the Week 6 visit. At the Final Visit the goals will be assessed based on levels of achievement on a 5-point scale. Investigators will be trained on goal setting/goal assessment and monitored for ability in key domains of goal setting (eg, attainability of goals, use of observable objectives and benchmarks, equidistance of scaling, general level of difficulty, goal differentiation, and overall quality).

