6.2 Justification for Study Design, Dose, and Endpoints

6.2.1 Study Design

Clinical practice guidelines for the treatment of MDD suggest changing the antidepressant after unsuccessful treatment with the initial antidepressant. An open-label, single-arm, multicenter, prospective, phase 4, interventional, flexible-dose study was chosen because this type of study design is designed to better understand if vortioxetine is effective in achieving outcomes that matter to subjects, improves quality of life, and is an effective strategy to treat MDD when current antidepressant is not adequate. The single-arm design allows each subject to serve as their own "control" in comparing baseline assessments with those performed at Week 12.

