5.0 ANALYSIS ENDPOINTS

The GAS, adapted for MDD is being used as primary endpoint in this study. As this is an adaptation of an existing instrument the results will provide novel outcome data for the goal attainment literature. Therefore, secondary endpoint assessments with validated instruments will provide additional confirmation of the effectiveness of vortioxetine in treating MDD when current antidepressant treatment is not adequate.

The following outcome measures will be used for secondary and exploratory endpoints as they are frequently used to assess clinical response: PHQ-9, PDQ-D, Quality of Life and Enjoyment and Satisfaction Questionnaire (Q-LES-Q), 5-item World Health Organization Well-Being Index (WHO-5), Clinical Global Impression-Severity (CGI-S), Clinical Global Impression-Improvement (CGI-I), Company Confidential Information

Measures have been taken regarding the methodology of this study to assess suicidal risk. The selection criteria exclude the participation of subjects at significant risk for suicide. Throughout the study, signs of suicidal risk will be assessed both by rating scale assessment (C-SSRS) and by investigators' clinical judgment. Subjects will be withdrawn from the study in case of such risk. Furthermore, subjects will be screened for the history of suicidal behavior.

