7.0 METHODS OF ANALYSIS AND PRESENTATION

7.1 General Principles

This is an open-label study with a single treatment regimen and all comparisons are made to the conditions prior to the subject being switched to vortioxetine.

Baseline values are defined as the last observed value before the first dose of study switch medication.

All statistical analyses will be conducted using SAS® Version 9.2, or higher.

All confidence intervals, statistical tests, and resulting P-values will be reported as 2-sided and will be assessed at $\alpha=0.05$ significance level unless otherwise stated. P-values will be rounded to 3 decimal places prior to assessment of statistical significance.

Means and medians will be presented to 1 more decimal place than the recorded data. The standard deviations (SDs) will be presented to 2 more decimal places than the recorded data. Confidence intervals about a parameter estimate will be presented using the same number of decimal places as the parameter estimate.

Where appropriate, variables will be summarized descriptively by study visit. For the categorical variables, the count and proportions of each possible value will be tabulated. The denominator for the proportion will be based on the number of subjects who provided non-missing responses for the categorical variable. For continuous variables, the numbers of subjects with non-missing values, mean, median, SD, minimum, and maximum values will be tabulated.

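### The objectives credit vortioxetine with goal achievement, but one uncontrolled arm of goal setting plus a switch supports only a description of outcome after that package

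*Protocol*

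**What the plan says.** - **Primary objective.** Protocol 5.1.1: "To determine the effectiveness of treatment with vortioxetine on subject goal achievement after a change in antidepressant medication for the treatment of MDD". It is repeated in Protocol 2.0 and 13.1.3 and in SAP 4.1 and 7.8. The secondary and additional effectiveness objectives (Protocol 2.0, 5.1.2, 5.1.3; SAP 4.2, 4.3) take the same form.
- **Aim.** Protocol 4.2 gives what the trial should show: "the process of Goal Attainment Scaling in MDD in conjunction with a change in antidepressant treatment to vortioxetine is effective in achieving outcomes".
- **Design.** Protocol 6.1: "This study is an open-label, single-arm, multicenter, prospective, phase 4, interventional, flexible-dose study". All subjects set three goals at Baseline.
- **Comparison.** Protocol 6.2.1: "The single-arm design allows each subject to serve as their own" control, a word the protocol itself puts in quotation marks and ties to Baseline against Week 12. SAP 7.1 says "all comparisons are made to the conditions prior to the subject being switched to vortioxetine".
- **Secondary endpoints.** SAP 5.0: "secondary endpoint assessments with validated instruments will provide additional confirmation of the effectiveness of vortioxetine in treating MDD". Protocol 6.2.3 says the same. The analysis is by paired t-tests (Protocol 13.1.3, SAP 7.8.4).
- **Primary analysis.** A responder proportion with a 95% CI and no formal test (Protocol 13.3, SAP 6.0).

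**The concern.** The rationale and the objective name different interventions. The rationale evaluates a package, goal setting together with the switch. The objective evaluates the drug.

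Goal setting is not only a measuring device here. Protocol 4.2 describes it as a way to align clinician and patient on what treatment is for, and Protocol 9.3.5 collects satisfaction with it as a means of better communication. It could therefore change the outcome by itself. Since every subject receives it, its contribution never varies independently of the drug.

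At stake is the study's conclusion. A report that follows the objective and the confirmation sentence could state that vortioxetine was effective for goal achievement, backed by significant before-after tests. The design can show how many subjects reached their goals, and how much scores changed, after the package was given.

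**Working it through.** **1. The plan's own figure.** Inputs from Protocol 13.3 and SAP 6.0: p = 0.50, n = 100, 95% two-sided. Half-width = 1.96 × √(0.5 × 0.5 / 100) = 0.0980, which matches ±0.098. The interval at the planned rate is 0.402 to 0.598. This is the precision of one arm's proportion; it holds no information on cause.

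**2. What the proportion says about the drug.** Let r be the responder rate that the same subjects would have had with goal setting but without vortioxetine. The part due to vortioxetine is 50% − r. The documents give no value for r, so it is an assumption, treated as fixed and taken over 0% to 50%:

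| Assumed r | Part due to vortioxetine (points) | With the 95% limits of the responder rate |
|---|---|---|
| 0% | 50 | 40.2 to 59.8 |
| 20% | 30 | 20.2 to 39.8 |
| 40% | 10 | 0.2 to 19.8 |
| 50% | 0 | −9.8 to 9.8 |

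The same observed result fits every row.

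**3. Whether Baseline serves as a control for the primary endpoint.** The SAP 7.8.1 formula with weights 1, 2, 3 and ρ = 0.3 has denominator √(0.7 × 14 + 0.3 × 36) = √20.6 = 4.539. With all goals at level x, the score is 50 + 60x / 4.539:
- x = −2 gives 23.6
- x = −1 gives 36.8
- x = 0 gives 50.0

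The documents do not state the level at which goals start. If it is −1 or −2 (assumption), the Baseline responder rate is zero by construction. Any later attainment, from any cause, then counts as response. The endpoint is a Week 12 cut-off and has no comparator.

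**4. Whether Baseline serves as a control for the secondary endpoints.** A within-subject comparison removes stable differences between subjects. It does not remove anything that changes with time: natural course, expectation in an open-label setting, goal setting, or the after-effects of stopping the earlier drug. Regression to the mean also remains possible. Entry requires PHQ-9 of at least 5 and CGI-S of at least 4 (Protocol 7.1), and when Screening and Baseline are combined the qualifying score is also the Baseline score.

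**5. Whether another section supplies the missing reference.** Protocol 4.1.1.2 cites placebo-controlled evidence, but from fixed-dose studies of 6 to 8 weeks and without mention of goal attainment. SAP 7.10 sets the interim responder rate against 50%, but gives no source for that figure and does not present it as a rate expected without vortioxetine. Neither can apportion the result.

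**The case against.** The strongest reply is that the operative plan is already descriptive. The primary endpoint is worded as an estimate, no hypothesis is tested, no success rule is set, and the title declares a single open-label arm. Such a design is legitimate in phase 4, and efficacy against placebo is cited as established. SAP 7.8.4 already says that the t-tests are applied to changes from Baseline. All of this stands. It limits the point to the objectives and their interpretation; the design, the estimate and its precision are untouched. It does not remove the objective's attribution to vortioxetine or the confirmation sentence, which remain in both documents.

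A reader might infer more than the documents support:

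- *That the earlier drug is removed at the same moment as goal setting.* The notes to the design schematic place discontinuation before Baseline, and Protocol 7.1 admits subjects who stopped up to 6 weeks before Screening. Stopping the earlier drug remains a competing explanation, but the steps are not simultaneous.
- *That goals on sexual dysfunction or weight gain measure side effects of the earlier drug.* The goal list as a whole is described as "representing MDD residual symptoms, antidepressant side effects, and common reasons for a change in antidepressant medication", without saying which item is which. Reasons for the switch are collected per subject; no visible text records a cause for each goal.
- *That the own-control sentence claims a contrast for the responder proportion.* It refers only to Baseline against Week 12 assessments.
- *That the ease of reaching significance measures bias.* With n = 100, an observed mean change of 1.984 / √100 = 0.198 SD is significant. That is a threshold for the secondary tests. A true change of 0.20 SD would be detected only about 51% of the time, and 80% power needs 0.283 SD. None of these figures says how much change is not due to the drug.

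**Conclusion.** The point holds as a mismatch between the stated objectives and what the design can show. The responder proportion and the within-subject changes after goal setting and a switch to vortioxetine are estimable, the proportion with the planned ±0.098. Attribution of either to vortioxetine is not supported, and no section of either document supplies what is missing.

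The amount of misattribution cannot be computed. The table in the working shows only that a 50% responder rate is compatible with anything from 50 points to none being due to the drug, over an assumed range for r. A reader might go further and conclude that the study is uninformative or that vortioxetine had no effect; the documents support neither. The objectives and the confirmation sentences are wrong as written and should be corrected, at almost no cost.

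**What to change.** 1. Reword the primary objective wherever it appears (Protocol 2.0, 5.1.1, 13.1.3; SAP 4.1, 7.8), for example: *To estimate the proportion of subjects with a GAS response at Week 12 after GAS goal setting and a switch to vortioxetine.* Align the design paragraphs that repeat it (Protocol 2.0, 6.1; SAP 4.4).
2. Reconcile the response cut-off in the same edit. Protocol 5.2.1 and SAP 5.1 use at least 50; SAP 7.8.1 uses greater than 50. All goals exactly at level 0 score 50.0, so the two rules classify that subject differently.
3. Reword the secondary and additional effectiveness objectives (Protocol 2.0, 5.1.2, 5.1.3; SAP 4.2, 4.3) as change from Baseline after the switch.
4. In Protocol 6.2.3 and SAP 5.0, replace the confirmation phrase with *description of change over 12 weeks*.
5. In Protocol 6.2.1, qualify the own-control sentence: a within-subject before-after comparison that does not isolate a drug effect.
6. In SAP 7.8.4, state that the paired t-tests assess change from Baseline, not drug effect.

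A descriptive table of attainment by predefined goal category is optional. A separate split for side effects of the earlier drug should not be added, since no visible text records a cause for each goal.

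The cost is wording in two documents and a less favourable claim. Items 1 and 3 to 6 change no analysis, sample size or visit; item 2 settles which of two printed cut-offs applies.
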